## 6.5. Concomitant medications and vaccination

Medications (verbatim) collected according to protocol will be coded to preferred name using the GSK Drug dictionary.

*Data related to medications and concomitant vaccinations will be available in the corresponding Study Data Tabulation Model (SDTM) (panel Concomitant Medication). A listing of AESI with previous concomitant vaccination (after manual cleaning of typo) will be provided.*

## 6.6. COVID-19 assessment

*COVID-19 AEs (classified by Medical Dictionary for Regulatory [MedDRA] System Organ Class [SOC] and Preferred Term [PT] level for hospitalised cases) will be described along with all other AEs leading to hospitalisation or death (see section 6.9.2.2)*

*Any sensitive analysis due to the COVID-19 pandemic may be part of an additional analysis request if relevant.*

## 6.7. Protocol deviations

*Important protocol deviations and non-important protocol deviations which result in exclusion from the ATP cohort will be summarised.*

*Protocol deviations will be tracked by the study team throughout the conduct of the study. These protocol deviations will be reviewed to identify those considered as important.*

*In addition, separate summaries will be produced for protocol deviations related to the COVID-19 pandemic.*

## 6.8. Exposure description to EPI vaccines

EPI vaccines are those routine vaccines usually given at 6, 10 and 14 weeks of age and which could be DTP, DTP-HepB, DTP-HepB-Hib vaccine. The subjects who received at least one dose of EPI vaccine are the vaccinated subjects.

The coding of vaccine is under the Epidemiologist team (EPI) responsibility (See details described in specific guideline: [Vaccine study-specific Coding Guidelines](#)).

The number of subjects who received at least one EPI dose will be described according to study group as well as the number of doses, the source for vaccine history (i.e. individual vaccination cards, vaccination registers at the health care facilities and vaccination data collected during census rounds).

Moreover, the age at each dose administration and the time between doses will also be described using descriptive statistics.

## **6.9. Analysis of co-primary objectives**

### **6.9.1. Population**

The analysis of co-primary objectives will be done on the ATP cohort and will primarily include subject from AS. A secondary population will include the subjects from the active and enhanced hospitalisation surveillances for the computation of incidence for all children <5 years.

### **6.9.2. Co-primary endpoints**

#### **6.9.2.1. AESI**

- Each AESI will first be analysed separately after case ascertainment on confirmed cases (hospitalised cases) classified by MedDRA SOC and PT level and case definition, and grouped by body system overall:
  - According to principal investigator (PI) diagnosis (i.e. after first line laboratory ascertainment or second line laboratory if available) **for progress report (see section 6.9.3.1) and interim analysis**,
  - According to final diagnosis (external expert diagnosis or PI diagnosis if external expert diagnosis not available) **for interim and final analysis**.
- Note: The confirmed AESI cases are those AESI with an available ICD-10 code (i.e. variable ICD-10 code not equal to “Not confirmed”, as per convention in the case report form [CRF] guidelines).*
- AESI will also be grouped by body system as described in table 3 of the protocol:
  - Nerves and central nervous system: Acute Disseminated Encephalo-Myelitis (ADEM), encephalitis, Guillain-Barre Syndrome, Hypotonic Hyporesponsive Episode (HHE), general convulsive seizure
  - Hepato-gastrointestinal and renal system: intussusception, hepatic failure or renal insufficiency
  - Skin and mucous membrane, bone and joints system: juvenile chronic arthritis, Stevens-Johnson syndrome/toxic epidermal necrolysis, Henoch-Schonlein purpura, Kawasaki disease
  - Systemic diseases and haematology: diabetes mellitus type I, thrombocytopenia, anaphylaxis

### 6.9.2.2. Other AE leading to hospitalisation or death

Other AE leading to hospitalisation or death are those events different from the pre-defined AESI, meningitis and malaria. These AEs classified by MedDRA SOC and PT level for hospitalised cases will be **described**:

- According to PI diagnosis corresponding to the diagnosis at discharge **for progress report (see section 6.9.3.1) and interim analysis**,
- According to final diagnosis (external expert diagnosis or PI diagnosis if external expert diagnosis not available) **for interim and final analysis**.

*PTs will be grouped into medically relevant groups to provide aggregated incidence rates. Indeed, due to the varied reporting terminologies used, some related or similar medical conditions may be counted separately resulting in partial incidence rate calculation (e.g. bacterial pneumonia and pneumonia, iron deficiency anaemia and anaemia). A manual grouping will be done based on a review of all the MedDRA PTs by the Epidemiologists and a Physician.*

### 6.9.2.3. Aetiology-confirmed meningitis

Aetiology confirmed meningitis (first line laboratory results **for progress report** and final classification based on second line laboratory results and after external panel of experts' review) will not be grouped with other AESI and will be considered as a single endpoint.

## 6.9.3. Incidence of co-primary endpoints

### 6.9.3.1. Description of the events

The occurrence of the following endpoints will be regularly (every 6 months) reported in progress reports [[Progress Report](#)] on the total enrolled cohort for hospitalised cases and outpatient visits when applicable:

- Each AESI according to site diagnosis,
- Other AE leading to hospitalisation or death, according to site diagnosis
- First line laboratory meningitis diagnosis according to site diagnosis following protocol definition (i.e. Bacterial confirmed meningitis, probable meningitis, clinically suspected meningitis).
- Malaria cases reported during outpatient visit or at hospital:
  - Clinically diagnosed Malaria
  - Any uncomplicated malaria (including *P. falciparum* malaria)
  - Any severe malaria (including *P. falciparum* malaria)
  - Severe *P. falciparum* malaria
  - Severe *P. vivax*
  - Cerebral malaria

- Fatal malaria cases
- Death reported at hospital or at home classified by MedDRA PT from study conclusion.

The number of subjects (%) reporting at least once each endpoint as well as the total number of events listed above and the number of associated outpatient visits/hospitalisations will be presented for both AS and EHS by EPI vaccination status and by gender. MedDRA SOC and PT level will be displayed for those safety endpoints.

Progress reports will include individual listings and statistical tables. The same tables and listings will also be presented for the final report.

Descriptive data in the progress report will also be presented:

- The demographic census will be presented by study site and by age group according to gender and overall.
- The number of subjects enrolled will be presented by study site, by study group and according to EPI vaccination status.
- The evolution of enrolment will be presented separately for each study group.
- Population characteristics (age at informed consent, gender) will be described by study group according to EPI vaccine received.
- The number and percentage of subjects who received the EPI vaccine doses will be summarised for EPI vaccinated subjects by each study group according to gender and overall.

And descriptive analysis of quality indicators (see section 6.10.7) will be done:

- The percentage of subjects reporting abscess at injection site within 7 days (day of vaccination and 6 subsequent days) after each dose of the DTP/HepB/Hib vaccine will be reported for each dose and overall according to gender and overall.
- As negative control, the prevalence of foot positional deformations will be presented according to gender and overall.

Of note, each progress report will be done on uncleaned data and will present cumulative results. The same analysis will be performed for the interim analysis on cumulative cleaned data. ***The final analysis will be done only on confirmed cases according to the protocol case definitions.***

#### **6.9.3.2. Incidence following EPI vaccine or virtual vaccination**

Analyses of incidence following EPI vaccine or virtual vaccination will only be performed on children enrolled in the AS ATP cohort for each group (6-12 weeks and 5-17 months).

These analyses will be computed on each confirmed co-primary endpoints (see section 6.9.2) by dividing the number of study participants reporting at least one event over the

follow-up period by the total person-time. A 95% CI will be computed using an exact method for a Poisson variable. Incidence per 100,000 person-years will be presented by study sites and overall.

Incidence Rates (IRs) after the primary schedule (i.e. combining the 3 doses) and the virtual secondary schedule (i.e. primary schedule and the virtual dose 4) will be presented.

### Individual follow-up period and at risk period

The total person-years will be computed as the sum of individual follow-up periods expressed in years. The computation of follow-up periods is defined in [Table 2](#).

For each endpoint, the follow-up period will be calculated separately depending on the at-risk period and the vaccine administration. The at-risk period will follow any dose, with a censoring of subjects when they receive the following dose.

**Table 1      Definition of at-risk period for AESI**

AESI	Risk period identified (for other licensed vaccines)*	Risk period applied
ADEM	NA	6 weeks
Encephalitis	6 weeks and 2 weeks	
Guillain-Barre Syndrome	3-5 days to 6-10 weeks	3 months
Generalized convulsive seizures	0-7 days	2 weeks
Hypotonic Hypo responsive Episode	immediately to 48h	2 weeks
Intussusception	1 to 7 days	2 weeks
Hepatic Insufficiency	1-10 days	2 weeks
Renal Insufficiency	1-10 days	2 weeks
Juvenile Chronic Arthritis	≤6 months	6 months
SJS & TEN	1-3 weeks	6 weeks
Henoch Schonlein purpura	NA	6 months
Kawasaki Disease	1 month	6 weeks
Diabetes mellitus type 1	≤6 months	6 months
Anaphylaxis	0-48 hours	2 weeks
Thrombocytopenia	12-25 days	6 weeks

\* from Table 3 of the protocol

Of note:

- The predefined list of AESI with expected at-risk period is available in the current Table 3 of the protocol,
- The at-risk period of 12 months will be used for meningitis,
- For other AEs leading to hospitalisation or death:
  - ***IR will only be computed on the 10 most frequent AEs following the grouping done by the Epidemiologists and a Physician (see section 6.9.2.2).***

- An at-risk period of 7 days and 30 days will be applied. Other risk periods may be defined with the support of the GSK Safety Physicians and the panel of experts.

**Table 2** Follow-up period definition after each dose

Risk period applied	Start	Stop earliest (i.e. date of censoring is whichever occurs first)
2 weeks	Reference date*	
 
• Date of first diagnosis of event of interest
 
• Date of death
 
• Date of next dose
 
• Date of end of risk period
 
• Date of last contact**
 
• Date of migration
 
• Date when child reaches 5 years or end of the study
 

6 weeks		
3 months		
6 Months		
12 Months		

\*Reference date: see definition detailed in section [7.2.2](#)

\*\* Date of last contact: see definition detailed in section [7.2.13](#)

Notes:

- a child may come back into the study after a certain period of lost-to follow-up. In such a case, the person-year will only consider the duration when the child was present on site (e.g. from reference date to migration date, then from immigration date to the end). To do so, a migration date will be derived using migration date from:
  - Date of migration:
    - From Study continuation
    - From Study conclusion
A return date will be derived using return date from:
  - Date of return:
    - From Study continuation
    - From Study conclusion
In case of several migrations/returns, several migration/return dates will be computed. For such subjects, the last contact date will be computed according to migration/return dates.
In case of any inconsistencies regarding the migration/return dates, the return will not be considered and the subject will be censored at the first migration date.
- If the ICF is signed after the first reference date, the individual follow-up period will be computed as the difference +1 between the follow-up end date and the ICF date. The follow-up end date remains the same as for subjects with ICF signed before the first reference date.

When AESI will be grouped, in case of multiple cases for a subject, only the first event will be considered in this analysis.

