Rationale and background	
GSK Biologicals has developed a pre-erythrocytic Plasmodium (P.) falciparum malaria vaccine, RTS,S/AS01_E, for routine immunisation of infants and children living in malaria-endemic countries of sub-Saharan Africa (SSA). RTS,S/AS01_E will be the first vaccine to be implemented for the prevention of malaria and it will be the first AS01-adjuvanted vaccine used in the paediatric population.
 
In July 2015, the European Medicines Agency (EMA) issued a positive opinion for the RTS,S/AS01_E vaccine, and in October 2015 recommendations about RTS,S/AS01_E were issued by the World Health Organization (WHO)'s Strategic Advisory Group of Experts (SAGE) on Immunization and the Malaria Policy Advisory Committee (MPAC). In April 2017, the WHO Regional Office for Africa announced that the RTS,S/AS01_E vaccine will be first introduced in 3 countries (Ghana, Kenya and Malawi) through a WHO-coordinated pilot implementation programme, referred to as the Malaria Vaccine Implementation Programme (MVIP) in the remaining sections of this document.
 
The safety and efficacy of RTS,S/AS01_E have been evaluated during pre-authorisation clinical trials conducted mainly in SSA.
 
The RTS,S/AS01_E vaccine will be implemented only in malaria endemic countries of SSA. Most of these countries have no baseline incidence data on rare diseases such as those that may be reported as adverse events (AE) following vaccination.
 
Data generated from EPI-MALARIA-002 VS AME (115055) (referred to as EPI-MAL-002 in the remainder of the document) will fill this gap and provide data that serve as baseline data for the post-implementation safety study (EPI-MAL-003) that will evaluate the safety of RTS,S/AS01_E as reflected in the co-primary and secondary objectives. Therefore, the primary

CONFIDENTIAL

115055 (EPI-MALARIA-002 VS AME)
Protocol Amendment 7 Final

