9.7.5. Analysis of co-primary objectives**9.7.5.1. Analysis population**

The population will include the subjects from the active surveillance of the EPI-MAL-002 study.

A secondary population will include the subjects from the active and enhanced hospitalisation surveillance of the EPI-MAL-002 study, computing incidence for all children < 5 years.

9.7.5.2. Statistical approach**9.7.5.2.1. Incidence of AESI, and other AE leading to hospitalisation or death**

The incidence rate of each AESI and other AE leading to hospitalisation or death will be calculated by dividing the number of subjects reporting at least one event over the follow-up period by the total person-time. A 95% CI will be computed using an exact method for a Poisson variable. The at-risk period will follow any dose, with a censoring of subjects when they receive the following dose. The minimum at-risk period for the analyses is 2 weeks. All AESI expected to occur between 0 day and 13 days following

CONFIDENTIAL

115055 (EPI-MALARIA-002 VS AME)
Protocol Amendment 7 Final

dose administration (see [Table 3](#)) will be analysed with an at-risk period of 2 weeks. The at-risk period of 6 weeks will be used for AESI expecting to occur between 14 days and 6 weeks. Finally, at-risk periods of 3 months, and 6 months will be for the AESI expected to occur between 6 weeks and 3 months, and between 3 months and 6 months, respectively. For other AE leading to hospitalisation or death the at-risk period for the analyses will be defined with the support of the GSK safety physicians and the panel of experts. In addition, the distribution of the Time-to-Onset of events after vaccination will be described, and additional at-risk periods will be considered based on the results as sensitivity analyses.

The person-time for an event of interest (e.g. juvenile chronic arthritis) will be calculated as the time between the reference date (date of first administration of DTP/HepB/Hib vaccine or date of first virtual vaccination, corresponding to the week before first visit) and the end of the at-risk period or the earliest of the followings:

- Date of first diagnosis of event of interest (e.g. first episode of juvenile chronic arthritis).
- Date of end of study period.
- Date of enrolment in EPI-MAL-003 (when applicable).
- Date when child reaches 5 years.
- Date of last contact (Lost-to follow-up).
- Date of death.

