#### 6.9.3.3. Incidence in children < 5 years

The IR of each and any AESI, of each and any other AE leading to hospitalisation or death (classified by the MedDRA SOC and PT level) and of aetiology confirmed meningitis will be estimated in all children < 5 years per 100,000 person per year. A 95% CI will be computed per year and overall using an exact method for a Poisson variable.

The numerator will be the number of cases of specified events (i.e. AESI) during the study period (in both AS and EHS grouped) and the denominator will be the person-years contribution of children in all communities < 5 years of age. The denominator will be computed using the census data. A census done at least once a year will provide the total number of children under 5 years.

For example, considering 5 census done between January 2015 and January 2017, a first subject recruited in March 2015 and a last subject recruited in April 2017:

The person-year (PY) will be computed as:

$$PY = N1 \cdot \text{Period1} + N2 \cdot \text{Period2} + N3 \cdot \text{Period3} + N4 \cdot \text{Period4} + N5 \cdot \text{Period5}$$

Contrary to the computation of IR following EPI vaccine or virtual vaccination where only the first event is counted in the numerator, for IR in children < 5 years, in case a subject had more than once the same AESI, all events will be counted in the numerator.

Confidence intervals [CI] will be computed using the exact method [[Clopper, 1934](#)].

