**Table 5 List of analyses by endpoints**

	Description of events	Incidence following primary and secondary schedule	Incidence for children < 5 years	Cumulative probability	Analysis of risk factors on IR following primary/secondary schedule	Incidence following:	Analysis of risk factors on IR	Prevalent rate
AESI according to Final diagnosis								
AESI (by MedDRA SOC & PT)	○/●	-	-	-	-	-	-	-
AESI by case definition as listed in CRF	○/●	○	●	○	○*	-	-	-
AESI grouped by body-system	○/●	○	●	-	-	-	-	-
Other AE leading to hospitalization or death according to Final diagnosis								
Other AE leading to hospitalisation or death (by MedDRA SOC & PT)	○/●	-	-	-	-	-	-	-
Other AE leading to hospitalisation or death (Aggregated)	-	○	●	-	-	-	-	-
Meningitis according to Final diagnosis								
Aetiology confirmed meningitis	○/●	○	●	○	○*	-	-	-
Aetiology confirmed, and/or probable meningitis	○/●	○	●	-	-	-	-	-
Probable meningitis	○/●	○	●	-	-	-	-	-
Aetiology Confirmed and/or probable and/or suspected meningitis	○/●	○	●	-	-	-	-	-
Malaria according to Final diagnosis								
Any Malaria	○/●	-	-	-	-	○	○	-
P. falciparum Malaria	○/●	-	-	-	-	○	○	-
Severe Malaria	○/●	-	-	-	-	○	○	-
P. falciparum severe Malaria	○/●	-	-	-	-	○	○	-
Cerebral Malaria	○/●	○	●	○	○*	○	○	-
Death (overall and by gender)								
Death all cause	○/●	○ a	●	○	○*	○	-	-
Death due to an AESI (all grouped)	○/●	○ a	●	○	-	○	-	-
Death due to another AE (all grouped)	○/●	○ a	●	○	-	○	-	-
Death due to meningitis	○/●	○ a	●	○	-	○	-	-
Death due to malaria (including P. falciparum malaria)	○/●	○ a	●	○	-	○	-	-
Death due to P. falciparum malaria	○/●	○ a	●	○	-	○	-	-
Hospitalisation								
Hospitalisation all causes	○/●	○ a	●	○	-	○	-	-
Hospitalisation due to malaria (including P. falciparum malaria)	○/●	○ a	●	○	-	○	-	-
Hospitalisation due to P. falciparum malaria	○/●	○ a	●	○	-	○	-	-
Anaemia								
Anaemia	○/●	-	-	-	-	-	-	○
Severe anaemia	○/●	-	-	-	-	-	-	○
Febrile convulsions								
Febrile convulsions	○/●	○	-	-	-	-	-	-
Surveillance indicator								
Foot positional deformations as a birth defect	○	-	-	-	-	-	-	-
Abscess at the injection site	○	-	-	-	-	-	-	-
● Analysis to be done for AS and EHS			Primary objective					
○ Analysis to be done only for AS			Secondary Safety objective					

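### SAP 6.9.3.2 limits the co-primary post-vaccination rates of other AEs to the ten most frequent groups, a cut that the protocol does not make and SAP section 9 does not declare

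*SAP*

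**What the plan says.** - **Protocol 9.7.5.2.1:** "The incidence rate of each AESI and other AE leading to hospitalisation or death will be" obtained as participants with at least one event over person-time, with an exact Poisson 95% CI. No frequency limit is set. The section also refers to rates for individual AEs and presents other AEs by MedDRA system organ class (SOC) and preferred term (PT).
- **SAP 6.9.3.2** (active surveillance, ATP cohort) opens in the same spirit: "These analyses will be computed on each confirmed co-primary endpoints (see section 6.9.2"). The notes under Table 1 then narrow it: "IR will only be computed on the 10 most frequent AEs following the grouping". The windows are 7 and 30 days.
- **SAP 6.9.2.2** on forming the groups: "A manual grouping will be done based on a review of all the MedDRA PTs by the Epidemiologists and a Physician". The reason given is that similar conditions reported under different terms would otherwise split a rate.
- **SAP 1 (Document history):** the limit belongs to Amendment 2 (14 March 2022). The stated purpose is a lighter final analysis after experience with the interim, and compliance with the sponsor's recommendations on the number of outputs.
- **SAP 9 (Changes from protocol)** lists the dropped risk-factor models for other AEs, but not this limit.
- **SAP 6.9.3.3** (all children under five) promises the rate "of each and any other AE leading to hospitalisation or death (classified by the MedDRA SOC and PT level"). In **SAP Table 5** the SOC and PT row has a description mark only. The incidence marks, both after the schedules and under five, sit in the row "Other AE leading to hospitalisation or death (Aggregated").
- **SAP Table 7** (interim) does mark post-vaccination incidence for other AEs by SOC and PT.

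**The concern.** The study exists to supply background rates for EPI-MAL-003, and other AEs are a co-primary endpoint in their own right. Cutting the list by observed frequency means that the set of estimates reported depends on the data and on an unstated ranking rule. A group outside the top ten would have no rate in the post-vaccination windows when EPI-MAL-003 needs one for comparison. The final analysis would also give less on this endpoint than the interim did. Because the limit is missing from section 9, a reader of that section would not learn that a co-primary analysis has been narrowed.

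**Working it through.** **1. The texts side by side.** Protocol 9.7.5.2.1 and the opening of SAP 6.9.3.2 call for a rate for each event; the note under SAP Table 1 allows ten. Those two pairs conflict directly. SAP 6.9.3.3 is a different analysis: active plus enhanced hospitalisation surveillance, census denominator, all events counted. The amendment history assigns the top-ten limit to 6.9.3.2 only. The conflict that involves 6.9.3.3 is with Table 5: rates by SOC and PT in the text, an aggregated row in the table.

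**2. What the ranking leaves open.** SAP 6.9.3.2 reports by age group, by site and overall, for two windows and two schedules. It does not say whether the ten are chosen per age group, per site or pooled, nor whether frequency is counted inside the windows or over all follow-up.

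**3. Reproducing the plan's precision figures.** Exact Poisson limits for x events in PY person-years are χ²(0.025; 2x)/2 ÷ PY and χ²(0.975; 2x+2)/2 ÷ PY.
- Protocol Table 6, 6-week window, 10,000 children: PY = 2×10,000/12 + 2×10,000×6/52 = 3,974.36. One event gives 25.2 per 100,000 PY [0.6, 140.2], as printed.
- Protocol Table 7: PY = 11,500×5×2 = 115,000. With 25 events the rate is 21.7 [14.1, 32.1], as printed.
- All 15 rows of Table 6 and all 4 rows of Table 7 reproduce.

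**4. Person-years in the windows for other AEs.** Assumptions: 10,000 children per age group, four reference dates, no loss, doses 1 and 2 censored at 28 days.
- 7-day: 10,000×4×7/365.25 = 767 PY.
- 30-day: 10,000×(28+28+30+30)/365.25 = 3,176 PY. Without the censoring it is 10,000×120/365.25 = 3,285 PY; for the three-dose primary schedule alone, 10,000×(28+28+30)/365.25 = 2,355 PY.

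**5. Expected events per age group (rate × PY).**

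| True rate per 100,000 PY | 7-day, 767 PY | 30-day, 3,176 PY | Under five, 115,000 PY |
|---|---|---|---|
| 1 | 0.008 | 0.03 | 1.15 |
| 50 | 0.38 | 1.6 | 57.5 |

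At 1 per 100,000 PY the chance of seeing at least one event is 0.8% in the 7-day windows, 3.1% in the 30-day windows and 68% in the under-five analysis. At 50 per 100,000 PY the 30-day chance is 80%. The 1.6 becomes 1.64 without censoring (3,285×50/100,000) and 1.18 for the primary schedule alone (2,355×50/100,000).

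**6. What an unreported row would look like.** In the 30-day windows, one event gives 31.5 per 100,000 PY [0.8, 175.4] and five give 157.4 [51.1, 367.4]. These are wide, but Protocol Table 6 itself displays rows for 1, 3 and 5 events, so the plan treats such counts as worth an interval.

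**The case against.** The strongest case against the point has five parts.

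- **Grouping is reasoned.** SAP 6.9.2.2 explains why rates by single PT would be fragmented. This stands, and the point is not a plea for PT-level rates in the windows. It justifies grouping, however, not stopping at ten groups.
- **The rule was fixed before the end of data.** Amendment 2 predates the site follow-up limits of April to July 2022 in SAP 7.2.13, and its reason is on record. That also stands: nobody picked the ten groups by hand. But the groups are formed from the reported terms, and the ranking basis is open.
- **Nothing inferential is at stake.** Correct: no test or vaccine contrast is attached to these rates, so no error rate is affected.
- **Other information remains.** Counts by SOC and PT are kept, and 6.9.3.3 as written gives under-five rates. But counts are not windowed rates. The under-five figure belongs to the secondary population, has a census denominator and counts repeat events. Table 5 also leaves unclear which rows it will have.
- **Rare events are not what is lost.** A reader might put the top-ten rule beside the rationale in the Protocol Abstract, "Most of these countries have no baseline incidence data on rare diseases", and infer that the SAP removes the rare events the study was set up to baseline. The documents do not support that. The protocol attaches its figure of about 1 per 100,000 PY to AESI; every AESI and every meningitis class keeps its rate without a cut. At that rate the capped windows would show almost nothing anyway.

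A reader might also infer that the top-ten sentence contradicts 6.9.3.3. It does not govern that section.

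**Conclusion.** The point holds as an undeclared and under-defined limit on a co-primary estimate in its primary population, made for output volume. It departs from protocol 9.7.5.2.1 and from the opening of SAP 6.9.3.2 itself. The mismatch between 6.9.3.3 and Table 5 is a second, separate defect.

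The cost is moderate. It falls on groups of intermediate frequency ranked 11th or lower, for which about one or two events per 10,000 children in the 30-day windows would go without a rate or interval. The size rests on an illustrative rate of 50 per 100,000 PY and on the assumptions in step 4. The documents give no event counts, so which groups would rank below tenth is unknown. That EPI-MAL-003 will want the same windows is inferred from the protocol's statement that events are monitored the same way in both studies; its own protocol was not available. The change should be made, though the study's main AESI and meningitis results do not depend on it.

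**What to change.** - In an appendix, give count, person-years, rate and exact Poisson CI for every medically grouped other AE and for any other AE combined, for the 7-day and 30-day windows and for children under five.
- Use the top ten only to choose what is highlighted in the text, and state the ranking basis: pooled or by age group and site, in-window or whole follow-up.
- Make SAP 6.9.3.2, 6.9.3.3 and Table 5 agree on the level of reporting (group, or SOC and PT), and define the aggregated row.
- Enter any limit that remains in SAP section 9, with its reason.

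The cost is a longer appendix: the same program run over more rows, with no new data and no change to the AESI or meningitis analyses.
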